6.1.3 Intention-to-Treat (ITT) Analysis Dataset

All randomised participants who received at least one dose of IP and have an evaluable baseline and post-baseline blood sample (at least one post baseline dose of RV3-BB). Participants will be analysed according to the treatment to which they were randomised. All analyses performed using the ITT set will be considered supportive.

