6.1.4 Per-protocol (PP) Analysis Dataset

All participants from the ITT population who completed the study in compliance with the protocol and who reported no major violation of the study protocol which may have effect on the primary endpoint. Participants will be analysed according to the treatment to which they were randomised. Primary analyses will be performed on the PP set.

7. General considerations

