7.1.4 Statistical tests

A single analysis will be performed at the end of the trial. No interim analyses are planned.

Primary Analysis:

The primary analysis and primary sensitivity analysis are based on the per protocol population defined as participants who receive all 3 doses of RV3-BB and have no major protocol violations (after reviewed and agreed at the end of the study). Thirty percent of participants are expected to be excluded from the PP population due to death, study withdrawal, loss to follow-up, or study non-compliance.

Non-inferiority of the lower titre vaccine will also be assessed in the intention to treat population. The cumulative probability of response by 18 weeks of age will be estimated by the Kaplan-Meier method for each vaccine arm. The difference between high and low titre arms in the cumulative probabilities and its 95% confidence interval will be calculated. If the upper bound of the confidence interval is below 20%, non-inferiority of the lower titre vaccine will be demonstrated.

Additionally, we will calculate the 95% CI of the binomial proportions using the method of Newcombe-Wilson without continuity correction and generalized estimating equations (GEE) after dose 3 on the PP and ITT analyses set.

All the primary and primary sensitivity analysis will be based on PP and ITT analysis set.

See section 10 for additional details.

Secondary Analyses:

Immunogenicity and vaccine-take results will be (inferentially) analysed as done for the primary analysis. Descriptive analyses are described in section 10.

Safety

No formal statistical testing will be performed on the safety data.

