8.1.1 Sample size

With the high titre RV3-BB neonatal vaccine schedule as the active control arm, the sample size is calculated to demonstrate the non-inferiority of the lower titre vaccine arms with respect to the proportion of participants who have a serum IgA response, 4 weeks after 3 doses of vaccine. A non-inferiority margin of 20% for the difference between arms will be used.

The primary analysis is based on the per protocol population defined as participants who receive all 3 doses of RV3-BB and have no major protocol violations. Thirty percent of participants are expected to be excluded from the PP population due to death, study withdrawal, loss to follow-up, or study non-compliance. Among those in the PP population, a 50% response probability is assumed for the active controls. Based on a one-sided 0.025 level score test with 90% power under the alternative of no difference in response probabilities, 172 participants per arm are required for a total sample size of 688 participants.

8.1.2 *Multicentre studies*

Approximately 688 babies will be randomised across three sites in Malawi. Study visits will be conducted at the sites or at participant homes.

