The cumulative vaccine take and the components of vaccine take (i.e. secondary endpoints) will be estimated similarly,

All summary and listing of immunogenicity data will be based on the FAS, ITT and PP populations. All the primary endpoint, primary sensitivity and secondary endpoint efficacy analysis will be based on the PP and ITT populations.

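### The SAP contradicts itself on which analysis set decides non-inferiority and never says which confidence interval is compared with the 20-point margin

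*SAP*

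**What the plan says.** **Analysis set.** SAP 6.1.4 says "Primary analyses will be performed on the PP set". SAP 6.1.3 says "All analyses performed using the ITT set will be considered supportive". Protocol 13.2 agrees on both, and SAP 8.1.1 and the first sentence under Primary Analysis in 7.1.4 also name PP. Two current sentences say otherwise. Near the end of the same block in 7.1.4 stands "All the primary and primary sensitivity analysis will be based on PP and ITT analysis set", and at the end of 9.1.2 "All the primary endpoint, primary sensitivity and secondary endpoint efficacy analysis will be based on the PP and ITT populations".

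**Success rule.** In 7.1.4 the rule (upper 95% limit below 20%) comes straight after the sentences on the ITT population and the Kaplan-Meier difference by 18 weeks of age. Protocol 13.1 has the same sequence.

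**Method.** SAP 9.1.2 gives, in order:
- a response-rate difference with a 95% interval of unnamed type;
- Kaplan-Meier by 18 weeks;
- the 20% rule, for an interval it does not identify;
- Newcombe-Wilson after dose 3, introduced as an addition;
- GEE after dose 3, on a logit model whose coefficient differences are described as log odds ratios.

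Section 7.1.4 refers to section 10 for further detail, but section 10 covers participant disposition.

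**Sizing.** SAP 8.1.1 fixes the margin ("A non-inferiority margin of 20% for the difference between arms will be used") and supposes that half of the high-titre arm responds. The test used for sizing is given as "Based on a one-sided 0.025 level score test with 90% power under the alternative of no difference in response probabilities". No score test of the difference is among the planned analyses.

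**The concern.** A non-inferiority conclusion needs one interval, from one set at one time point, fixed before unblinding. Here the set called supportive carries the only explicit success rule in 7.1.4, while the set called primary has no named interval. If PP fails and ITT passes, or the reverse, each side can point to a sentence in the SAP. The answer is then undefined in borderline cases, and the type I error depends on how the text is read.

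The listed analyses are also not versions of one quantity. Kaplan-Meier runs to 18 weeks of age. The primary objective is response 4 weeks after three doses. In the neonatal arms dose 3 is given at about week 10, so that time point is about week 14.

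**Working it through.** **1. The plan's own figure.** Inputs from SAP 8.1.1: control response 0.50, true difference 0, margin 0.20, one-sided 0.025, power 90%, 30% excluded from PP.

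n = (1.960 + 1.282)² × (0.25 + 0.25) / 0.20² = 10.507 × 0.50 / 0.04 = 131.3, so 132 evaluable per arm. Then 132 × 1.30 = 171.6, so 172. The stated figure is reproduced. The PP set to be expected under the plan's 30% exclusion is 172 × 0.70 = 120.4, taken as 120 per arm. (Whether the 30% should be added or divided out is a separate question.)

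**2. One dataset, two verdicts.** PP responders 60/120 (high titre) and 51/120 (lower titre), difference 0.075.
- Wald, which equals Kaplan-Meier with Greenwood variance when follow-up is complete: 0.075 + 1.960 × √(0.5×0.5/120 + 0.425×0.575/120) = 0.075 + 1.960 × 0.06419 = 0.2008. Non-inferiority is not shown.
- Newcombe-Wilson: the Wilson upper limit for 0.500 is 0.5881 and the Wilson lower limit for 0.425 is 0.3402. The upper bound is 0.075 + √(0.0881² + 0.0848²) = 0.1972. Non-inferior.

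**3. How often verdicts differ.** Simulation with 400,000 trials per scenario, control response 50%, PP of 120 per arm nested in ITT. The documents give no ITT size; 145, 160 and 172 per arm are assumed. Outcome definition and response rate are the same in both sets, follow-up is complete, and GEE is left out.

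| Quantity (%) | ITT 145 | ITT 160 | ITT 172 |
|---|---|---|---|
| True deficit 10 points: Newcombe on PP and on ITT disagree | 13.6 | 18.2 | 19.9 |
| True deficit 10 points: Newcombe and Wald disagree, PP only | 3.3 | 3.3 | 3.4 |
| No difference: Newcombe on PP and on ITT disagree | 6.2 | 8.0 | 8.4 |
| No difference: Newcombe and Wald disagree, PP only | 2.5 | 2.5 | 2.5 |
| True deficit 20 points: PP Newcombe passes | 2.6 | 2.7 | 2.6 |
| True deficit 20 points: any of four passes (Newcombe or Wald, PP or ITT) | 3.8 | 4.0 | 4.1 |
| True deficit 20 points: Newcombe passes on both sets | 1.7 | 1.5 | 1.3 |

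Most of the disagreement comes from PP against ITT. The choice between two interval methods on PP adds little.

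**4. GEE.** A 20-point deficit is an odds ratio of (0.30/0.70)/(0.50/0.50) = 0.43 at a 50% control rate, but (0.20/0.80)/(0.40/0.60) = 0.375 at 40%. A log odds ratio cannot be compared with 20 points without a conversion, and the SAP gives none.

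**The case against.** The strongest reply is that the hierarchy is visible. PP is named primary in several places in both documents, ITT is labelled supportive, and 7.1.4 brings ITT in as something also assessed. Section 9.1.2 states the 20% rule without mentioning ITT and introduces Newcombe-Wilson after it as an addition, with GEE following, so both look supplementary. The sentences naming both sets may mean only that each analysis is run twice. Section 9.1.1 defines response in the neonatal arms over doses 1 to 3, so the Kaplan-Meier curve might be meant to stop there.

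Much of this stands. A reader might infer that the SAP names no primary set, or that three methods on two sets are six equal candidates for the verdict. The documents do not support that: the set problem is a contradiction within a mostly consistent text, and the order in 9.1.2 points to Newcombe-Wilson and GEE as supplements.

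It does not close the gap. If those two are supplements, what remains is an unnamed interval or Kaplan-Meier, and 7.1.4 ties Kaplan-Meier to ITT and to 18 weeks. No sentence chooses between them or says what happens when sets or methods disagree.

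**Conclusion.** The plan should be corrected. As written, it contradicts itself on whether ITT can establish non-inferiority and leaves the deciding interval unidentified. PP and ITT verdicts by the same method would differ in about 14 to 20% of trials at a true 10-point deficit and in 6 to just over 8% at no difference. On PP alone, Newcombe and Wald differ in only about 3%. These figures rest on 120 PP infants per arm, an assumed 145 to 172 in ITT, equal response in both sets and complete follow-up. They do not model responses gained between weeks 14 and 18.

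A reader might infer that the plan inflates the false non-inferiority rate to about 4%. That holds only if the best of several results is taken, which 6.1.3 speaks against. Requiring both sets to pass would be conservative (1.3 to 1.7%), and PP Newcombe alone is close to nominal (about 2.6%). The supportable statement is that the error rate depends on a reading the SAP does not fix. Nor should the figure be added up over the two lower titres and set against 2.5%: most of that rise comes from making two comparisons, which is a separate matter and would remain with a single deciding analysis.

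**What to change.** In SAP 7.1.4 and 9.1.2, name one deciding analysis for each lower-titre contrast:
- PP set;
- IgA response at 4 weeks after dose 3, stating that a response after any earlier dose counts, because the objective is cumulative;
- difference high minus lower titre, with a two-sided 95% interval by one named method;
- non-inferior if the upper limit is below 20 points.

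The Newcombe-Wilson interval already planned is adequate. A score interval matching the sizing test is an acceptable alternative, but a matter of preference.

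Keep Kaplan-Meier, GEE and all ITT analyses, labelled as sensitivity or supportive and unable by themselves to establish non-inferiority. Reword the two sentences that name both sets to say this. Simply deleting ITT from them would also remove the ITT sensitivity and secondary analyses. Move the success rule so that it follows the PP analysis, correct the reference to section 10, and record the clarification in SAP section 5, since Protocol 13.1 has the same placement of the rule.

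The cost is wording only, with no new data. The sponsor gives up the option of claiming success from a supportive set or method.

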2.1.2 Secondary objectives

The secondary objectives of this study are:

- To assess the cumulative anti-rotavirus serum IgA response (defined as a ≥3-fold increase from baseline) 4 weeks after 3 doses of RV3-BB administered in an infant schedule at a vaccine titre of 1x10⁷.
- To assess cumulative vaccine take and components of vaccine take after 3 doses of RV3-BB (titre of 1x10⁷) administered in a neonatal schedule versus three doses of RV3-BB in an infant schedule at a vaccine titre of 1x10⁷.
- To assess cumulative vaccine take and the components of RV3-BB vaccine take after 3 doses of RV3-BB administered as a neonatal schedule at a vaccine titre of 1x10⁷, 3x10⁶ or 1x10⁶.
- To assess cumulative vaccine take and components of vaccine take after 2 doses of RV3-BB administered as a neonatal schedule at a vaccine titre of 1x10⁷, 3x10⁶ or 1x10⁶ or 2 doses as an infant schedule at a vaccine titre of 1x10⁷.
- To assess cumulative vaccine take and components of vaccine take after the first dose of RV3-BB administered as a neonatal schedule at a vaccine titre of 1x10⁷, 3x10⁶ or 1x10⁶ compared to placebo (1st dose of IP in the infant schedule).
- To assess cumulative vaccine take and components of vaccine take after the first dose of RV3-BB at a vaccine titre of 1x10⁷, 3x10⁶ or 1x10⁶ in the neonatal schedule compared with the first dose of RV3-BB at a vaccine titre of 1x10⁷ in the infant schedule.
- To describe the geometric mean titre of the anti-rotavirus serum IgA response after 3 doses of RV3-BB administered as a neonatal schedule or an infant schedule.

- To describe the safety and tolerability of RV3-BB when administered as an infant or as a neonatal schedule.
- To describe the occurrence of diarrhoea episodes in participants, according to severity and detection of wild-type rotavirus.

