9.1.1 Variables and derivations

Primary endpoint:

A serum IgA response in the *neonatal* schedule, is defined as $a \ge 3$ -fold increase from baseline, where baseline is defined as stated in sections 7.1.2 and 8.1.3 for handling of missing baseline IgA measurements of this analysis plan.

Secondary endpoints:

- A serum IgA response in the *infant* schedule, is defined as a ≥ 3-fold increase from baseline, where baseline is defined as stated in sections 7.1.2 and 8.1.3 for handling of missing baseline IgA measurements of this analysis plan.
- Cumulative vaccine take is defined as vaccine take observed at the current assessment time point or following any previous dose, where vaccine take is

defined as \geq 3-fold increase in serum anti-rotavirus IgA from baseline to post IP dosing, or detectable RV3 shedding in stools (by ELISA or PCR) any day from day 3 to 5 following administration of IP.

- Shedding of RV3-BB is defined as presence of RV3-BB shedding in stool from days 3-5 following each dose of IP.
- Geometric mean titre of the anti-rotavirus serum IgA response after 3 doses of RV3-BB.
- Safety and tolerability (as per sections 15 to 16 of this analysis plan) of RV3-BB.
- Occurrence of diarrhoea episodes in participants, according to severity and detection of wild-type rotavirus.

Derivations:

A participant will, at each vaccine titre, be defined a "responder" if he/she has a serum *IgA response* (\geq 3-fold increase in serum anti-rotavirus IgA from baseline) for neonatal arms IP dose 1 - 3 and infant arm IP dose 2 - 4 of RV3-BB. The response rate will be dichotomised (0 = non-responder, 1 = responder).

Geometric means (and associated summary statistics) will be determined as follows:

- 1. Log-transform the titre data (if not already log-transformed)
- 2. Determine the arithmetic mean and other descriptive statistics of the transformed data using the PROC MEANS procedure
- Exponentiate the output obtained from the PROC MEANS procedure, depending on data to be presented (log-transfer vs not log-transformed)
- 9.1.2 Analysis

Non-inferiority of lower titre vaccines (primary as well as secondary endpoints):

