The difference between high and low titre arms in the response rate and its 95% confidence interval will be calculated. The cumulative probability of anti-rotavirus serum IgA response (as defined above) by 18 weeks of age will be estimated by the Kaplan-Meier method for each vaccine arm. PROC LIFETEST (SAS[®] Version 9.4 or above) will

be used to analyse the response rates (non-responder *vs.* responder). With the CENSOR variable, 1 is commonly used to indicate that an event occurred (subject is a responder) and 0 indicates that the event did not occur (the subject was censored/is a non-responder).

Non-inferiority of the lower titre vaccine will be demonstrated if the upper bound of the confidence interval is below 20%.

Additionally, we will calculate the 95% CI of the difference between vaccine groups in the serum IgA response rate after dose 3 using the method of Newcombe-Wilson without continuity correction for the difference between binomial proportions as implemented in PROC FREQ (SAS® Version 9.4 or above).

Generalized estimating equations (GEE) will be used to analyse the response rates (non-responder vs. responder) after dose 3 using PROC GEE (SAS® Version 9.4 or above). We will calculate a binary outcome ($1 = \ge 3$ -fold increase, 0 = < 3-fold increase from baseline) after dose 1, 2, and 3 for each participant who received vaccine according to the neonatal schedule. After that, we will fit a model with dose as a discrete/categorical/factor variable, vaccine group (low, medium, high dose) as a discrete variable, and dose by vaccine group interaction term. The model will use the binomial distribution for the outcome variable and the exchangeable correlation matrix to account for the correlation between a participant who received vaccine according to the neonatal schedule outcomes. Model will be used for the analysis. Once the model is fit, contrast statements will be used in PROC GENMOD (SAS® Version 9.4 or above) to calculate the difference in the response rate after dose 3 for the high versus low dose and so forth.

In the table, (Estimate, standard error, 95% CI) will be presented.

The general linear model to be fit by GEE is

 $logit(p_{ij}) = \beta_{ij}$

where p_{ij} is the response rate after the i-th dose in the j-th vaccine group. Differences between the β s represent the log odds ratio in response rates.

MCRI-RV3-BB-004

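### The SAP's only stated inference for vaccine take is the lower-titre non-inferiority analysis, so three comparative secondary objectives (placebo, infant schedule, first active infant dose) have no difference or confidence interval

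*SAP*

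**What the plan says.** SAP 7.1.4 (Secondary Analyses) gives the inferential instruction for these endpoints: "Immunogenicity and vaccine-take results will be (inferentially) analysed as done for the primary analysis". It sends the reader to section 10 for the descriptive analyses, but section 10 is participant disposition; the immunogenicity analyses are in section 9.

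SAP 9.1.2 holds the inferential methods. Its opening line reads "Non-inferiority of lower titre vaccines (primary as well as secondary endpoints", and it specifies:
- one named contrast, high versus lower titre;
- one decision rule: "Non-inferiority of the lower titre vaccine will be demonstrated if the upper bound of the confidence interval is below 20" per cent;
- a GEE for participants vaccinated on the neonatal schedule, with "vaccine group (low, medium, high dose) as a discrete variable";
- for vaccine take: "The cumulative vaccine take and the components of vaccine take (i.e. secondary endpoints) will be estimated similarly".

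SAP 2.1.2 (and Protocol 4.2) sets three objectives with other comparators:
- each neonatal titre after its first dose, "compared to placebo (1st dose of IP in the infant schedule";
- the high titre "administered in a neonatal schedule versus three doses of RV3-BB in an infant schedule at a vaccine titre of" 1x10⁷, after three doses;
- the first dose at each titre "in the neonatal schedule compared with the first dose of RV3-BB at a vaccine titre of" 1x10⁷ on the infant schedule.

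SAP 9.1.5 defines baseline and cumulative take after three doses for each schedule. SAP 9.1.6 and 9.1.7 give frequency tabulations after two doses and after one. Protocol 13.3.2 left secondary analyses, multiplicity and Type I error to the SAP, which contains no multiplicity rule.

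**The concern.** A cross-reference to the primary analysis works only if the secondary question has the same arms and the same kind of hypothesis. Here it does not. The primary question is whether a lower titre loses too much against the high titre. The placebo question is whether a dose produces take at all, and the other two compare schedules. If the SAP does not name the arms, the time point and the summary for these contrasts, that choice is left until the data are in hand, or the contrasts go unreported.

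The dose-1 contrast matters most. Every arm receives three active doses overall, so IP dose 1 offers the trial's only randomised, same-age comparison of RV3-BB with placebo before the placebo arm starts active vaccine.

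**Working it through.** **1. Objectives against stated analyses**

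| Objective (SAP 2.1.2) | Fits the 9.1.2 contrast (high vs lower titre)? | Infant arm in the GEE? | What else the SAP gives |
|---|---|---|---|
| Neonatal titres compared, three doses | Yes | Not needed | 9.1.2 in full |
| Each neonatal titre vs placebo, IP dose 1 | No | No | 9.1.7: frequencies, correct comparator named |
| High-titre neonatal vs infant schedule, three doses | No | No | 9.1.5: definitions only |
| First neonatal dose vs first active infant dose | No | No | No dedicated section |

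The last three rows carry no named difference, interval, hypothesis or error control. SAP 9.1.11 lists a neonatal-versus-infant comparison of geometric mean titre, but without a method, and it does not concern take.

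**2. The baseline for the dose-1 placebo contrast**

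SAP 7.1.2 sets the infant-arm IgA baseline as the serum taken before the second dose. In the schedule of procedures, that Visit 3 sample is also the only serum taken between IP dose 1 and IP dose 2, so it is the post-dose-1 measurement too. The fold rise in a placebo infant is then x/x = 1, which can never reach 3. The IgA component would be zero in the placebo group by construction, and the contrast would favour vaccine whatever the dose did. The opening of SAP section 9 uses cord blood for what it calls the neonatal comparison. That would solve the problem, but the SAP does not say that the placebo contrast belongs under that label.

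**3. Could the 20-point rule be carried over to placebo? (hypothetical)**

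Inputs: 172 per arm and 30% excluded from the per-protocol set (SAP 8.1.1), so 172 × 0.7 = 120.4, taken as 120 per arm. More infants may be evaluable after dose 1. The interval is Newcombe-Wilson without continuity correction (SAP 9.1.2). Placebo take rates are assumptions.

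Formula: with p1 and p2 the observed proportions and (l, u) their Wilson limits, the interval for p1 − p2 runs from (p1 − p2) − √[(p1 − l1)² + (u2 − p2)²] to (p1 − p2) + √[(u1 − p1)² + (p2 − l2)²].

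Example with no effect, 12/120 in both arms: Wilson limits are 0.058 and 0.167. The upper bound is 0 + √[(0.167 − 0.100)² + (0.100 − 0.058)²] = 0.079. That is below 0.20, so the rule is met although the vaccine added nothing.

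Summing over all outcomes of two independent binomials with equal true rates:

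| True rate in both arms | P(upper bound of placebo − vaccine < 0.20) | P(lower bound of vaccine − placebo > 0) |
|---|---|---|
| 10% | 0.999 | 0.023 |
| 20% | 0.974 | 0.024 |
| 28% | 0.938 | 0.025 |
| 50% | 0.890 | 0.023 |

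**4. Can the data answer the placebo question?**

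Using the same interval, read as lower bound above 0, power at 120 per arm is 0.978 for 30% vs 10% and 0.945 for 50% vs 28%. For example, 36/120 vs 12/120 gives a difference of 20.0 points, 95% CI 10.0 to 29.7.

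**The case against.** The strongest reply is that no passage plans a wrong test. The 20-point rule is worded for the lower-titre vaccine only. The opening line of SAP 9.1.2 extends it to further endpoints, not to further comparators. Placebo is not a titre, and the GEE could not include it. SAP 9.1.7 names the placebo infant group correctly and is openly descriptive. A reader might infer from SAP 7.1.4 that vaccine is to be judged non-inferior to placebo, or that these objectives are tested against the high-titre arm. The documents do not support either inference. This part of the reply stands, and it makes the pass probabilities above an illustration only.

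The reply continues that the cross-reference carries over methods: Newcombe-Wilson is described for the difference between vaccine groups in general, SAP section 5 speaks of comparisons involving the neonatal schedule, and Protocol 13.3 sets a two-sided 5% default. This is a fair reading of intent, but it does not close the gap. The arms, dose, baseline and error control for the three contrasts would still have to be chosen at analysis.

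Two further cautions are right. The 28% rate is 2/7 Phase I placebo infants aged 6 to 8 weeks, under a definition that also counted neutralising antibody and day 3 to 6 shedding, so it is not a forecast for placebo neonates here. And the objectives are worded as assessments without a stated hypothesis, so descriptive intervals would be an acceptable answer.

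**Conclusion.** The point holds as a gap in specification. The one inferential analysis stated for vaccine take does not fit three of the comparative secondary objectives. For these the SAP gives definitions or frequency tables at most, and nothing dedicated to the first-dose comparison between schedules. As written, none has a planned difference or confidence interval.

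This does not touch the primary analysis, and it should be corrected rather than treated as a fatal fault. The baseline finding follows directly from SAP 7.1.2 and the visit schedule. The pass probabilities of 0.94 to 0.999 (120 per arm, placebo rates of 28% to 10%) rest on assumed rates and describe a test that the SAP does not plan. They show only why the rule should not be borrowed.

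**What to change.** In SAP 7.1.4 and 9.1.2:

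1. State that the 20-point rule applies only to mid or low titre versus high titre on the neonatal schedule.
2. For the three other contrasts, name the arms and the dose. Report the difference in cumulative take and in each component with the Newcombe-Wilson two-sided 95% CI, without the 20-point rule.
3. For each neonatal titre versus placebo after IP dose 1, read the interval for a difference (lower bound of vaccine minus placebo above 0), in line with the protocol's two-sided 5% default. Either state how multiplicity across the three titres is handled or declare the intervals descriptive.
4. For that contrast, use the cord or Visit 1 sample as the IgA baseline in both groups, with the same handling of missing and high cord values in each.
5. Correct the section 10 reference in 7.1.4.

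The cost is SAP wording and a few more PROC FREQ outputs. No new data, samples or participants are needed.
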